2.2 Primary and Secondary Aims

The primary aim (Aim 1) of the Aspire to Better Health study is to test the efficacy of a smartphone app plus health coaching intervention targeting weight loss vs. an attention control condition utilizing a device which tracks sleep.

The secondary aim (Aim 2) is to examine mediating variables of the intervention delivery on percent weight loss at 6 and 12 months. The mediators include adherence to self-monitoring, levels of discrimination, and dietary and physical activity (PA) self-efficacy. Finally, the third aim (Aim 3) will explore potential moderators of percent weight loss at 6 and 12 months, including depressive symptoms, ideal body image, and motivation for behavior change.

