2.6 Sample Size and Randomization

A sample size of 256 participants (n=128 per each trial arm) will have sufficient power (80%) to detect an

average between-group difference with a moderate effect size of Cohen's $d = 0.4$. The mixed effect modeling for repeated outcome measures at 6 and 12 months was used for the power calculation using two-sided significance level of 0.05 assuming 1) first-order autoregressive covariance structure, 2) the within-structure correlation of 0.8, and 3) 20% attrition rate at 12-month follow-up. After completing the informed consent and baseline data collection, participants will be randomly assigned 1:1 to the intervention or the attention-control group. Stratified randomization by sex (female vs. male) and ethnicity (Non-Hispanic Black vs. Hispanic Black) will be used. For each sex-ethnicity stratum, randomization will occur in permuted blocks of varying block sizes. The advantage of permuted block randomization is that it will ensure balance in the number of participants in the two trial arms during the entire study period.

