Aim 2: We denote X = Independent variable, Y = Outcome measures, and M = Potential mediator. Mediation will be tested through first showing that X (e.g. intervention) is associated with both M (e.g., dietary self-efficacy) and Y (e.g., % weight change) using mixed-effects regression models as described above. Then, we will sequentially model the effect of X on Y, without and with adjusting for potential mediators. At last, we will use mediation path analysis to simultaneously regress (a) Y on M and X, and (b) M on X.. Estimates for the mediation effect will be derived using delta method or bootstrapping method if lack of normality is evident.²⁸ Adequacy fit of the path model is indicated by a non-significant χ^2 statistic, Comparative Fit Index (CFI) and Tucker-Levis Index (TLI) ≥ 0.9 , and a root mean square error approximation (RMSEA) ≤ 0.08 .

Aim 3: Similarly, we specify X = independent variable (e.g., intervention), Y = outcome variables (e.g., % weight change), and W = potential moderator (e.g., depressive symptoms). We will then test the significance of the moderating effect by including the interaction term of X and W in the mixed-effects regression models. A significant interaction between X and W suggest that the effect of X on Y changes at different levels of W.

Missing data: We will carefully examine the pattern of missing data and conduct appropriate multiple imputation if data are missing at random. If missing not at random is indicated, pattern mixture modeling will be used instead. Sensitivity analysis will be used to evaluate the robustness of study findings under different methods.

7. Data Management

REDCap data collection projects rely on a study-specific data dictionary defined in an iterative self-documenting process. REDCap supports electronic signatures by positively identifying the user through a unique username and password combination. The provisioning of accounts for system authentication is

integrated with the OSU Wexner Medical Center (OSUWMC) LDAP authentication service for studies containing protected health information (PHI) and is secured behind the OSUWMC firewall.

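### The Aim 2 path model names no baseline covariates, so any baseline cause of both a mediator and weight change biases the indirect effect, even if it is balanced between arms

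*Combined protocol and SAP*

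**What the plan says.** Section 6, Aim 2, proceeds in three steps. It first shows that the intervention (X) is associated with the mediator (M) and with the outcome (Y), using the mixed models described for Aim 1. It then models X on Y without and with the mediators. Finally it fits a path model to "simultaneously regress (a) Y on M and X, and (b) M on X". The indirect effect is tested by the delta method, or by bootstrap if normality is lacking.

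The only covariate provision is in Section 6, Aim 1. It is attached to the mixed models, and its one example is imbalance between arms in baseline characteristics. The only sensitivity analysis in the plan concerns missing data.

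Section 4 has the Table 3 and Table 4 measures collected from all participants at baseline, before randomisation, and again at 6 and 12 months. They include weight, PHQ-9, TSRQ motivation, PROMIS emotional support and the self-efficacy and discrimination scales. Sex and ethnicity are stratification factors (Section 2.6). Section 2.2 gives the Aim 3 moderators as "including depressive symptoms, ideal body image, and motivation for behavior change".

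**The concern.** Participants are randomised to an arm, not to a level of self-efficacy, discrimination or self-monitoring. Suppose more motivated or less depressed students have higher self-efficacy and also lose more weight. Then M and Y are associated within each arm even if self-efficacy does nothing. A regression of Y on M and X attributes that association to M, and multiplying it by the arm effect on M yields an indirect effect that is not mediation. Balance between arms does not prevent this, because the association arises within arms.

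Aim 2 is the stated secondary aim. What is at stake is its explanation of why the intervention works: a mediator could be credited with weight loss that has another source. This is a separate matter from when the mediator is measured relative to the outcome.

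**Working it through.** **Inputs from the documents (Section 2.6).** "A sample size of 256 participants (n=128 per each trial arm"; "two-sided significance level of 0.05"; standardised effect 0.4; "the within-structure correlation of 0.8"; "20% attrition rate at 12-month follow-up".

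**The plan's own figure.** It concerns Aim 1 only; no power or error figure is given for Aim 2. After 20% loss, 128 × 0.8 = 102.4 per arm. At a single time point, power = Φ(0.4 × √(102.4/2) − 1.96) = Φ(2.862 − 1.96) = Φ(0.902) ≈ 82%. Averaging two visits correlated 0.8 gives an SD of √((1 + 0.8)/2) = 0.949 and power of about 85%. The stated 80% is met, so 204 completers and a total effect of 0.4 SD are fair inputs for Aim 2.

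**Assumed inputs.** The documents give none of these:
- arm effect on the mediator, a = 0.2, 0.4 or 0.6 SD
- true effect of M on Y, b = 0
- one baseline common cause U, correlated r with both M and Y within arm, r = 0.2, 0.3 or 0.4, balanced in expectation by randomisation

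**Size of the bias.** With M and Y at unit variance within arm, the coefficient of M in the regression of Y on M and X is b + r². With b = 0, the spurious indirect effect is a × r². At a = 0.4:
- r = 0.2: 0.4 × 0.04 = 0.016 SD (4% of a 0.4 SD total effect)
- r = 0.3: 0.4 × 0.09 = 0.036 SD (9%)
- r = 0.4: 0.4 × 0.16 = 0.064 SD (16%)

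Simulation returned the same means, and 0.00 with U in both equations. If mediation is real (b = 0.3, a = 0.4, r = 0.3), the true indirect effect is 0.4 × 0.3 = 0.12 and the model as written gives 0.4 × (0.3 + 0.09) = 0.156, which is 30% too large.

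**False-positive rate.** The test is the delta method, z = ab / √(a²·SE(b)² + b²·SE(a)²) with estimates in place of a and b. It is two-sided at 0.05, with 204 completers, b = 0 and 4,000 or more simulated trials per setting.

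| Arm effect on M | r = 0.2 | r = 0.3 | r = 0.4 | U adjusted |
|---|---|---|---|---|
| 0.2 SD | 0.4% | about 1% | about 7% | at most 1% |
| 0.4 SD | 2% | 8% | 29% | about 1% |
| 0.6 SD | 5% | 17% | 50% | about 3% |

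- If the plan's preliminary step (significant X–M and X–Y) must also be passed, the rates at r = 0.4 are 25% (a = 0.4) and 42% (a = 0.6).
- If the arm does not affect the mediator, the rate at r = 0.4 is about 0.5%.
- The delta method is conservative here. At a = 0.4, a joint-significance test gives about 8%, 19% and 51%, against about 4% adjusted. The percentile bootstrap, the plan's conditional alternative, gave about 7%, 19% and 52% (600 trials per setting).
- Modest causes add up. Three independent ones at r = 0.2 each give a spurious b of 3 × 0.04 = 0.12 and, at a = 0.4, a delta-method rate of about 15%.

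**Whether the fit criteria would catch it.** With one mediator, the equations use three free paths to fit three covariances. The model is saturated (0 degrees of freedom), so the χ², CFI, TLI and RMSEA criteria cannot reveal the confounding.

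**The case against.** The strongest reply is that the Aim 2 notation is schematic and that the Aim 1 covariate clause carries over, since Aim 2 refers back to the Aim 1 models. The clause is open-ended, so this is fair to a point. However, the reference back is attached to the preliminary mixed models and not to the path equations. The clause's only example, imbalance between arms, is also the wrong criterion: a common cause of M and Y is expected to be balanced by randomisation, so an imbalance rule would usually not select it.

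A second reply is that the size rests on assumptions. This stands. With the delta method, a single common cause at r = 0.2 keeps the error at about 5% or less throughout, and a small arm effect on the mediator keeps it low until r = 0.4. Discrimination is one of the four mediators, and the documents give no expected arm effect on it.

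Three stronger readings are tempting and are not supported:
- A reader might infer that the plan itself says motivation and depressive symptoms drive weight loss. Section 2.2 calls them only potential moderators, and Section 6 tests them as interactions with arm. Their direct effect on weight, and their link to the mediators, are plausible but not stated.
- A reader might take a false-positive rate of about one half as typical. With a 0.4 SD arm effect it needs r = 0.4 and either a joint-significance test, which the plan does not name, or the bootstrap, which it makes conditional. The delta method reaches it only with a 0.6 SD arm effect.
- A reader might assume the bias is always upward. That requires the common cause to act on M and Y in the same direction; with opposite signs it would be downward.

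**Conclusion.** The point holds as a defect in the specified path model. As written, the model omits baseline causes of both mediator and outcome, and no other text in the plan supplies them. The resulting indirect effect is biased by a × r² under the assumptions shown. At a 0.4 SD arm effect on the mediator this means 0.016 to 0.064 SD, and false mediation in about 2% to 29% of trials by the delta method. Across arm effects of 0.2 to 0.6 SD the range is 0.4% to 50%. After adjustment the rate is about 3% or less.

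The arm effects and correlations are assumptions, and the adjusted figures suppose that the common cause is measured without error. The documents do not show that false mediation will occur, only that the analysis has no protection against it. The Aim 1 comparison of weight loss is unaffected. This should be corrected before the mediation analysis is run, but it does not threaten the trial's primary conclusion.

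**What to change.** In Section 6, Aim 2:

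1. Name one prespecified set of covariates measured before randomisation, and enter it in both path equations and in the sequential models: the baseline value of the mediator where one exists (adherence to app self-monitoring has none), TSRQ motivation, PHQ-9, PROMIS emotional support, sex and ethnicity. Baseline weight is optional, since the outcome is already a percentage of it.
2. Select these as possible causes of both mediator and outcome, not by testing for imbalance between arms.
3. Add a sensitivity analysis showing how strong a residual unmeasured common cause would have to be to remove each indirect effect.
4. Report indirect effects as conditional on no unmeasured confounding of mediator and outcome.

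The cost is SAP wording and a few degrees of freedom out of about 204 completers; no new data are needed. Covariates remove only measured confounding, and questionnaire error leaves some of that behind, so steps 3 and 4 are needed as well.

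### Aim 2 defaults to the delta method and uses the bootstrap only on evident non-normality; this costs power for mediators with small-to-moderate paths, even with normal data

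*Combined protocol and SAP*

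**What the plan says.** Section 6 (Statistical Analysis), Aim 2, sets out three steps.

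- An entry step: "Mediation will be tested through first showing that X (e.g. intervention) is associated with both M (e.g., dietary self-efficacy) and Y".
- A sequence of models for the intervention effect on the outcome, without and then with the mediator.
- A path analysis: "we will use mediation path analysis to simultaneously regress (a) Y on M and X, and (b) M on X".

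On inference for the mediation effect it says: "Estimates for the mediation effect will be derived using delta method or bootstrapping method if lack of normality is evident". Because the bootstrap is conditional, the delta method is the default. The text does not say whether normality refers to the data, the residuals or the estimated effect. It also does not say how normality is judged or which bootstrap interval would be used.

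Section 2.2 names four mediators: adherence to self-monitoring, discrimination, and dietary and physical activity self-efficacy. Section 2.6 gives a power calculation for the between-group difference only. No path size or power is given for Aim 2.

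**The concern.** The path model estimates the mediation effect as a × b, where a is the effect of the intervention on the mediator and b is the effect of the mediator on the outcome given the intervention. The delta method attaches a standard error to a × b and treats the estimate as symmetric. In samples of this size the product of two estimated coefficients is skewed unless both are large relative to their standard errors. The skewness comes from the multiplication, so it is present when mediator and outcome are perfectly normal.

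A normality check on data or residuals therefore does not detect the problem. With normal data the check passes, the delta method stays, and the test of mediation is conservative. At stake is the chance of detecting true mediators in the secondary aim, when the plan already names a better-behaved alternative.

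**Working it through.** **1. The plan's own figure.** Section 2.6 gives 128 per arm, 20% attrition, d = 0.4 and a "two-sided significance level of 0.05". Completers per arm: 128 × 0.8 = 102.4, taken as 102. SE = √(2/102) = 0.140; 0.4/0.140 = 2.86; power = Φ(2.86 − 1.96) = 81.5%. This agrees with the stated 80%. It concerns Aim 1 only; there is no mediation figure to reproduce.

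**2. Inputs for the mediation check.** From the documents: n = 204 completers (2 × 102), 1:1 allocation, two-sided 0.05. Assumed, because the documents give none: path sizes a and b, with mediator and outcome residuals exactly normal with SD 1.

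**3. Why the delta test is conservative.** Its statistic is

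z = ab / √(a²·SE_b² + b²·SE_a²) = z_a·z_b / √(z_a² + z_b²).

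This is always smaller in size than both z_a and z_b. If the two are equal, each must reach 1.96 × √2 = 2.77 before the product is declared significant.

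Example with a = 0.4, b = 0.2: SE_a = 2/√204 = 0.140 and SE_b = 1/√204 = 0.070, so z_a = z_b = 2.86. The delta statistic centres on 2.86/√2 = 2.02, barely above 1.96. The chance that both paths are individually significant is about 0.815 × 0.815 = 66%, close to what an asymmetric interval achieves below.

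**4. Simulated power, normal data, n = 204.** The entry step is read as p<0.05 for both associations, with an assumed total effect of 0.4 SD.

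| a (SD) | b | Delta | Percentile bootstrap | Delta, after entry step | Bootstrap, after entry step |
|---|---|---|---|---|---|
| 0.4 | 0.2 | 43% | 63% | 35% | 50% |
| 0.5 | 0.2 | 59% | 76% | 49% | 62% |
| 0.4 | 0.3 | 75% | 84% | 63% | 69% |
| 0.8 | 0.3 | 99% | 99% | 80% | 80% |

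These are Monte Carlo figures and the last digits are not exact. At (0.4, 0.3), repeated runs gave 70% to 75% for delta and 79% to 84% for the bootstrap or a product-distribution interval. The gap was 9 to 11 points before the entry step and 6 to 7 after it.

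**5. Type I error, n = 204.** With a = 0.4, b = 0: 1.0% (delta) vs 3.9% (bootstrap). With a = 0, b = 0.3: 2.4% vs 5.1%. The bootstrap's extra power does not come from an inflated error rate.

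**6. Skewness and coverage.** Where both paths were non-zero, the estimated product had skewness of about 0.2 to 0.75. At a = 0.4, b = 0.2, the true effect lay above the delta interval in 6.9% of trials and below it in 0.6%. For the product-distribution interval the figures were 4.2% and 1.5%. So the delta method is conservative as a test of zero, but its interval tends to sit too low when mediation is real.

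**7. No direct effect.** The total effect is then only a × b, for example 0.4 × 0.2 = 0.08 SD, and 0.08/0.140 = 0.57 standard errors. The entry step rarely passes. Power after it is 4.6% (delta) vs 6.6% (product interval) at (0.4, 0.2), and 11.6% vs 12.2% at (0.4, 0.3).

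**The case against.** **The entry step limits the gain.** This stands. A reader might infer from the figures without it that the plan as written forgoes about 20 points of power. The documents do not support that, because mediation is tested only after the intervention is shown to be associated with mediator and outcome. At a total effect of 0.4 SD the gains fall to about 15, 13, 6 and 0 points across the four rows. With no direct effect the entry step is the larger cause of missed mediation.

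**The path sizes are chosen, not given.** This stands too. The gain runs from nil to about 20 points before the entry step, depending on the assumption.

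**Not every mediator fits the simulated case.** Table 4 defines adherence as a threshold on logged intake, tracked through Ascend, which is linked to Lose It!. Controls receive that app only at 12 months (Section 3.8). Analysed as a threshold, adherence is plainly non-normal, so the trigger could fire. Its intervention-to-mediator path should also be large, where the methods differ less: at a = 0.8, b = 0.14 and n = 204, 46% (delta) vs 52% (product interval). The distribution of the discrimination measure is unknown. The case applies best to the two self-efficacy scales.

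**The trigger might mean normality of the estimated effect.** The wording allows this, and such a rule would address the problem. It is therefore too strong to say the check is certainly unrelated to the skewness. But the text does not say so and gives no criterion, and the data or residuals are the more natural reading.

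**The error is in the safe direction.** True for false claims of mediation: the delta test makes fewer, not more. The cost is missed mediators.

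**Conclusion.** The point holds as a cheap improvement to a secondary aim. On the natural reading of the trigger, normal data leave a conservative test in place. At 204 completers it loses about 9 to 20 points of power for small-to-moderate paths before the entry step, about 6 to 15 points after it with a total effect of 0.4 SD, and essentially nothing when both paths are strong. With no direct effect the difference is about 2 points.

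These sizes rest on assumed paths, normal residuals with SD 1, and the entry step read as p<0.05. The documents supply only the sample size, attrition, allocation and significance level.

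A reader might go further and infer that Aim 2 is invalid or that the trial's main result is affected. Neither follows: the delta test does not inflate false positives, and Aim 1 does not use it.

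**What to change.** In Section 6, Aim 2:

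- Make a percentile bootstrap interval the primary interval for every indirect effect, whatever a normality check shows. Resample whole participants within arm, with at least 5,000 resamples. An equivalent asymmetric product-distribution interval would also serve.
- Remove the normality trigger.
- Report the delta-method result as secondary.
- State how the bootstrap is combined with the multiple imputation planned in the same section, including which is nested in which.

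The cost is SAP wording, computing time, and the work of specifying the last item. No change to sample size or data collection is needed.

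### The Aim 2 path model is saturated as written (df = 0), so its fit criteria are met automatically or cannot be computed and say nothing about model adequacy

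*Combined protocol and SAP*

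**What the plan says.** Section 6, Aim 2, sets up the notation: "We denote X = Independent variable, Y = Outcome measures, and M = Potential mediator". After preliminary regressions, the last step is a path analysis to "simultaneously regress (a) Y on M and X, and (b) M on X". The effect of interest has its own method: "Estimates for the mediation effect will be derived using delta method or bootstrapping method if lack of normality is evident".

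A fit rule follows: "Adequacy fit of the path model is indicated by a non-significant" chi-square, together with CFI and TLI of at least 0.9 and RMSEA of at most 0.08.

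Two places hint at something larger than one mediator. The preceding regression step says "we will sequentially model the effect of X on Y, without and with adjusting for potential mediators", in the plural. Section 2.2 gives a list of four ("The mediators include adherence to self-monitoring, levels of discrimination, and dietary and physical activity (PA) self-efficacy") and names percent weight loss at both 6 and 12 months. No joint path model is written out. The plan gives no path constraint, latent variable, residual covariance structure or degrees of freedom.

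**The concern.** Chi-square, CFI, TLI and RMSEA all measure how far the data contradict the restrictions a model imposes. The model in section 6 frees every possible path among X, M and Y, so it imposes no restriction and the data cannot contradict it.

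This rule is the only adequacy check stated for the Aim 2 path model. Arm is randomised but the mediator is not. The real threats to the mediation claim are therefore unmeasured common causes of M and Y, or weight change driving the mediator instead of the reverse. The listed indices cannot detect either. A report that the path model met all its fit criteria would read as support for the causal structure when that result was fixed in advance.

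**Working it through.** **Inputs.** The model is from section 6, Aim 2. The sample size (256) and 20% attrition are from section 2.6, giving 256 × 0.8 = 204.8, or about 205 completers. The plan gives no df to reproduce. Its one design figure is consistent: with 102.4 completers per arm and d = 0.4, power is Φ(0.4 × √(102.4/2) − 1.96) = Φ(0.90) = 0.817, against the stated 80%. The df result does not depend on it.

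**Degrees of freedom of the stated model.**
- Observed moments: p(p+1)/2 with p = 3, which is 6.
- Free parameters: three paths (X→M, M→Y, X→Y), the variance of X and two residual variances, which is 6.
- df = 6 − 6 = 0.

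**Each criterion at df = 0.**
- Chi-square is 0, because the fitted covariance matrix equals the observed one. No p-value exists on 0 df.
- CFI = 1 − max(χ² − df, 0)/(baseline misfit). The numerator is 0, so CFI is 1.
- TLI uses χ²/df = 0/0, and RMSEA = √[max(χ² − df, 0)/(df(N − 1))] is also 0/0. Both are undefined; software may print 1 and 0 by convention.

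**Simulation check.** At n = 205, 2,000 datasets were generated in each of five scenarios. Four had no indirect effect (X→M zero, M→Y zero, or both) and one had both paths at 0.5. The largest absolute chi-square was 1.8 × 10⁻¹³, zero to rounding. The mean estimated indirect effect was about 0 in the four null scenarios and 0.25 in the fifth. Fit was identical throughout, while the indirect effect separated the scenarios. Swapping M and Y gives another 6-parameter saturated model, also with chi-square 0.

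**Larger models the sponsor might have meant** (none is stated):

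| Model | Moments | Parameters | df |
|---|---|---|---|
| Four mediators, residual covariances free | 21 | 21 | 0 |
| Four mediators, residual covariances zero | 21 | 15 | 6 |
| One mediator, Y at 6 and 12 months, residual covariance free | 10 | 10 | 0 |
| Same, residual covariance zero | 10 | 9 | 1 |
| One mediator, three covariates in both equations | 21 | 21 | 0 |
| One mediator, three covariates in the Y equation only | 21 | 18 | 3 |
| M and Y at both times, each Y on same-time M and X, within-variable residual covariances free | 15 | 13 | 2 |

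**What the rule tests with parallel mediators and zero residual covariances.** With K mediators, df = K(K − 1)/2, and every restriction says that two mediators are uncorrelated given arm. For K = 2, χ² = −n ln(1 − r²) on 1 df and RMSEA = √[(χ² − 1)/(n − 1)]. The residual correlation r is assumed, because the documents give none. With n = 205:
- r = 0.1: −205 × ln(0.99) = 2.1, p = 0.15; RMSEA = √(1.06/204) = 0.07. Both pass.
- r = 0.2: −205 × ln(0.96) = 8.4, p = 0.004; RMSEA = √(7.37/204) = 0.19. Both fail.
- r = 0.4: −205 × ln(0.84) = 35.7; RMSEA = √(34.7/204) = 0.41. Both fail.

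CFI and TLI also depend on the other correlations and were not computed here. With four such mediators (df = 6), the simulated chi-square rejection rate at n = 205 was about 5% at r = 0, 67–70% at r = 0.1 and essentially 100% at r = 0.2 or more. It was much the same whether or not arm affected the mediators.

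**The case against.** The strongest reply is that fit does not decide mediation in this plan. The decision rests on the regressions and on the indirect effect by delta method or bootstrap. The fit sentence attaches no gate and no consequence to failure. That stands: no estimate, interval or p-value in Aim 2 changes because of it. A reader might infer that mediation will be declared whether or not it exists. The documents do not support that, and the simulated indirect effects above show the estimate behaving properly.

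Second, the X–M–Y notation may be a schematic. The outcome measures and mediators appear in the plural, two time points are named, and covariates are mentioned under Aim 1. Several larger models have positive df, so it would be too strong to say that the criteria can never fail under any model the sponsor might fit. But the plan writes out only the saturated model. Of the natural extensions, some are saturated too, and others become testable only through restrictions that the plan does not mention.

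Third, the correlations of 0.2 and 0.4 are not from the documents, and 205 completers sets aside the planned multiple imputation. Both are fair. The figures are illustrations; the df = 0 result needs neither. Using all 256 participants at r = 0.2 gives χ² = −256 × ln(0.96) = 10.5 and RMSEA = √(9.45/255) = 0.19, so the illustration does not turn on this.

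Finally, a sensitivity analysis for confounding is a different matter from degrees of freedom. That is true, and deleting one sentence would cure the narrow defect. The addition is recommended because deletion leaves the path model with no stated check on its main assumption.

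**Conclusion.** The point holds for the model as written. The path model has df = 0, so the chi-square and CFI criteria are met by construction, while TLI and RMSEA are undefined or set by software. This is algebra and rests on no assumed figure. The consequence is limited to false reassurance about the adequacy of a secondary-aim model; the indirect-effect estimates and the primary aim are untouched.

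If a joint model was intended, the plan has to say so. In the parallel-mediator version with zero residual covariances, the rule would test only whether the mediators are uncorrelated given arm. It could then reject a sound mediation model, as the example with an assumed correlation of 0.2 shows. It is a point to correct in the SAP; it does not threaten the trial.

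**What to change.** 1. Delete the chi-square, CFI, TLI and RMSEA rule for the single-mediator model, and report each indirect effect with its confidence interval.
2. In any model with several mediators, leave their residual covariances free.
3. Keep fit indices only for a model that is written out in full (mediators, time points, covariates, residual covariances), with its over-identifying restrictions and df named.
4. Because M is not randomised, add a sensitivity analysis that reports, for each indirect effect, the residual M–Y correlation that would bring it to zero.

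The cost is SAP wording and one short analysis on data already being collected.
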